11 PROTOCOL DEVIATIONS

Protocol deviations are defined as deviations from the study procedures, including but not limited to any violation of inclusion/exclusion criteria, assessments not performed or performed outside the scheduled time windows, or use of drugs that are known to affect study endpoints.

All protocol deviations will be entered into the clinical trial management system (CTMS) or other approved format.

All deviations will be reviewed and each deviation will be classified as major or minor; all major deviations will be further reviewed to determine whether or not the deviation impacts the evaluability of the subject for the primary objectives of the study and therefore should result in the subject being excluded from the PP Population at the time of deviation.

11.1 Major Protocol Deviations

Subjects with major protocol deviations will be identified (at a population level) to determine whether they will be excluded from any analysis population. This will take place during the pre-analysis data review meeting prior to database lock.

The categories for the major deviations may include, but are not limited to the deviations presented in **Table 12**.

**Table 12: Definition of Major Protocol Deviations**

Category	Description
Mis-randomization	An error in the randomization and/or product allocation process.
Product adherence	Confinement: Use of any nicotine or tobacco-containing product other than the assigned product, using the product distribution log. Ambulatory: Non-compliance in the CHTP 1.2 arm will be defined for each period. Non-compliance is based on product use reported in the product use diary for periods 2-4, as any of the following occurrences: – Use of more than 2 CC in a single day – Average product use from Day 1 through the end of the period is more than 0.5 CC per day.
Protocol violation	A deviation to the inclusion/exclusion criteria.
Procedural violation	A major deviation in the conduct of a procedure
Duration of 24 hour urine collection	Not all urine collected over 24 hours or collection period covers less than 20h or covers more than 28h for Day -2, Day -1, Day 1, Day 2, Day 3 or Day 4, Day 5/Discharge from Confinement, Day 30 Visit, Day 60 Visit or Day 90 Visit
Concomitant medication	Use of drugs which are known to affect CYP2A6 or CYP1A2 activity (except medication containing estrogen) or could interfere with clinical risk endpoints such as 11-DTX-B2..
Reporting of product use	Less than 75% of the daily product use reported in the e-diary over a period is available, or daily product use not reported over a period of more than 7 consecutive days
Visit missing	Scheduled visit not done

Subjects with violations of inclusion criteria 1, 2, 4 and 6, or of exclusion criteria 2 to 4, 15, 18 and 19 will be excluded from the PP Population. Other violations of the inclusion and exclusion criteria will be reviewed for their impact on the evaluability of the primary objectives during the pre-analysis data review meeting.

Single use of more than 2 CCs on a single day would exclude all measurements within a week after the deviation. The impacted subject would be classified as non-evaluable for the objectives assessed within a week after the deviation.

Average product use higher than 0.5 CC per day from Day 1 through an evaluation timepoint would exclude all measurements at that evaluation point. The impacted subject would be classified as non-evaluable for the objectives of the study at that evaluation point.

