12.3.2 Per Protocol Population

The PP population is a subset of FAS and includes all randomized subjects who fulfill key compliance criteria of the protocol, and have no major protocol deviation (to be further described in the SAP).

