10.5 Per Protocol Populations

The PP populations are subsets of the FAS and include, by period, all randomized subjects who fulfill key compliance criteria of the protocol in the respective period, and have no major protocol deviation impacting evaluability as defined in Table 12 (see Section 11“Protocol Deviations”).

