12.1.5 Handling of Dropouts or Missing Data (including outside the limits of quantification)

For laboratory parameters:

- Values below the lower limit of quantification (LLOQ) will be imputed using LLOQ/2. For values above the upper limit of quantification (ULOQ), the ULOQ will be imputed.
- The number of values below LLOQ or above ULOQ will be presented in each summary table. If 50% or more data are below LLOQ or above ULOQ, only the number (%) of value below LLOQ or above ULOQ will be reported in the summaries, together with minimum and maximum of the observed values.
- Missing data at Baseline will not be imputed.

For daily product use data:

- If at least 75% of the daily product use assessments over a period are available, with no more than 7-days of consecutive missing data:
 - Product use categories will be defined based on percentage of THS 2.2 use calculated by averaging non missing consumption data over the analysis interval.
 - Compliance to randomized product will be defined based on the available product use data.
- If less than 75% of the daily product use assessments over a period are available, or product use data is missing over a period of more than 7 consecutive days:
 - Product use category and Compliance to randomized product will be considered missing.

For MNWS, QSU-brief, and mCEQ questionnaire data:

- Total scores and domain or subscale scores will be derived by averaging the individual non-missing item scores if at least 50% are non-missing, otherwise they will be set to missing.

For missing or partial dates:

- Missing dates for Day 30, 60, and Day 90 Visits will be imputed for the calculation of product use exposure within periods by adding 30, 60, or 90 days to the randomization date. If the imputed date falls after discharge date (e.g. for early terminated subjects), then the discharge date will be used.
- Missing or Partial dates will not be imputed for Adverse Events (AEs), for medical history, and for concomitant medications, but assumptions will be made as follows to assign them to specific analysis categories:

Date information (*)	AE Category	Disease Category	Medication Category
Missing date or Partial date, (e.g., --May2012, or ----2011) if month/year is the same as, or later than the month and/or year of Screening.	Product-emergent	Concomitant disease	Concomitant medication

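### Does the undefined compliance condition in SAP 10.5 leave the analysis set for Day 90 total NNAL open?

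*SAP*

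**What the plan says.** Protocol 12.3.2 limits the PP population to subjects who "fulfill key compliance criteria of the protocol, and have no major protocol deviation (to be further described in the SAP". SAP 10.5 makes the sets period-specific. They "include, by period, all randomized subjects who fulfill key compliance criteria of the protocol in the respective period", and these subjects must also "have no major protocol deviation impacting evaluability as defined in Table 12"; the sentence ends with a reference to Section 11.

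Section 11 has major deviations reviewed to decide "whether or not the deviation impacts the evaluability of the subject for the primary objectives of the study", and exclusion from the PP population follows from that review. In the product-adherence row of Table 12, "Non-compliance in the CHTP 1.2 arm will be defined for each period". Two triggers are listed: more than two CC on any one day, and an average above 0.5 CC per day from Day 1 to the end of the period.

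Two paragraphs below the table give the consequences. For the single-day trigger: "Single use of more than 2 CCs on a single day would exclude all measurements within a week after the deviation", and the subject is "classified as non-evaluable for the objectives assessed within a week after the deviation". For the average, all measurements at the evaluation point concerned are excluded.

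SAP 12.5.1 makes PP periods 1 and 4 the primary sets for biomarkers of exposure. Table 7 runs period 4 from after the Day 60 Visit up to the Day 90 Visit. SAP section 10 says the biomarker tables will be repeated on the full analysis set (FAS) if it differs from the PP set.

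**The concern.** The protocol hands the PP definition to the SAP, and SAP 10.5 repeats the compliance wording without listing what it covers. The nearest per-period definition is the Table 12 adherence row. If that row fills the first condition, one day with three cigarettes anywhere in period 4 removes a CHTP 1.2 subject from the Day 90 NNAL analysis. If the paragraph below the table governs, the same day matters only when it falls in the week before the assessment.

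SAP 12.1.5 also speaks of compliance over a period: "Compliance to randomized product will be defined based on the available product use data".

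Total NNAL at Day 90 is a primary endpoint, and SAP 12.1.8 requires all primary endpoints to be significant before any confirmatory claim. One would want membership of its analysis set to be readable from the SAP. Two side points add to the unease. One week is shorter than one NNAL half-life. The table list in 13.3.1 shows the primary ANCOVA (Table 15.2.3.1) on the PP set only.

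**Working it through.** **1. How far the readings differ.** Period 4 covers Days 61 to 90, which is 30 days. The one-week rule reaches back to Day 83 or Day 84, depending on whether the seventh day counts. The readings therefore differ for a lapse on 22 or 23 days. With the ±5-day windows of Visits 3 and 4 the period lasts 20 to 40 days, and the differing days number 12 to 33.

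Example: three CC on Day 65 and none otherwise gives 3/90 = 0.03 CC per day, well under 0.5. The whole-period reading excludes this subject and the one-week reading keeps the value. The average rule does not settle the matter, since 0.5 × 90 = 45 CC are allowed.

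**2. Which reading the text supports.**
- Scheduled ambulatory assessments take place only at the Day 30, 60 and 90 Visits, so each ambulatory period has one assessment visit.
- The Day 60 and Day 90 Visits are at least 20 days apart. Any lapse in the week before the Day 90 Visit therefore lies inside period 4.
- If every day above two CC in the period already excluded the subject, the one-week paragraph could never exclude anything more.
- If Table 12 says what is major and the paragraphs below say what follows, every sentence has a use. Section 11 separates the two steps in this way, and SAP 12.2 tabulates deviations by category and by evaluability.
- SAP 12.1.5 is a missing-diary rule (75% of days available, no gap longer than 7 days). It sets no PP criterion.

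**3. The plan's own figure.** SAP Tables 9 to 11 use a mean ratio of 0.30, a CV of 0.60, a 50% reduction, one-sided 2.5%, and at least 50% of the 80 CHTP 1.2 subjects retained.
- SD on the log scale = √ln(1 + 0.60²) = 0.555; difference = ln(0.50/0.30) = 0.511.
- 40 v 40: SE = 0.555 × √(1/40 + 1/40) = 0.124, and 0.511/0.124 = 4.12. Power is 98.5% (normal) or 98.3% (noncentral t). The SAP states 98%.
- With fewer CHTP 1.2 subjects against 40 CC (noncentral t): 30 gives 96.4%, 20 gives 91.1%, 12 gives 78.4%.
- Against the stated null (ratio of 1 or more), power exceeds 99.9% in all of these cases.

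The documents give no lapse rate. If each day carried an independent chance p of more than two CC, retention out of 80 would be 80(1 − p)³⁰ under the whole-period rule and 80(1 − p)⁷ under the one-week rule. That is 59 v 75 at p = 0.01 and 44 v 69 at p = 0.02, all above the planned 40.

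**4. Carry-over under the one-week rule.** The half-life is 10 to 15 days in protocol 4.2 and 10 to 18 days in Appendix D. After 7 days, 2^(−7/10) = 62% to 2^(−7/18) = 76% of a lapse's increment remains. Assume first-order decay, with the CC steady state set to 1 and CHTP 1.2 at 0.30. A full usual smoking day 8 days before sampling then adds (1 − 2^(−1/h)) × 2^(−8/h):
- h = 10: 0.0670 × 0.574 = 0.0385, or 12.8% of 0.30.
- h = 18: 0.0278, or 9.3% of 0.30.
- If the cigarettes replace CHTP use one for one, multiply by 0.70: 9.0% and 6.5%.

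Suppose 10% to 50% of PP subjects each had such a day. The group ratio would move from 0.30 to between 0.30 × 1.065^0.10 = 0.302 and 0.30 × 1.128^0.50 = 0.319.

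**The case for a change.** The strongest reply is that SAP 10.5 states two conditions. Section 11's evaluability logic explains the second, but the first is separate and tied to the period, and no sentence says that the one-week rule replaces the Table 12 definition. That is literally true, and a one-line definition is missing.

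It does not make the whole-period reading a serious rival. The reference to Section 11 closes the sentence that contains both conditions. Tying compliance to the period fits SAP 12.1.7, which gives each product use period its own PP set. The first condition also keeps real content under the one-week reading, because the cumulative average and diary completeness still apply. Importing the whole adherence row into it would make the evaluability qualifier pointless for that row.

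A second argument is that the whole-period rule removes less adherent users from one arm and so favours CHTP 1.2. Exclusion for smoking CC in the ambulatory period applies to the CHTP 1.2 arm alone under either reading, so the readings differ in degree and not in kind.

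A third is the table list. It has no FAS version of Table 15.2.3.1 and shows NNAL on the FAS only descriptively. That mismatch stands, but section 10 already commits to the repeat, so it is a slip in the list and not a missing analysis.

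**Conclusion.** No change follows. The compliance wording in SAP 10.5 is a gap that an analyst fills sensibly from Section 11. A day above two CC is a major deviation, and it removes a CHTP 1.2 subject from the Day 90 NNAL analysis when it falls in the week before the assessment. The average-use, diary-completeness and other major-deviation rules apply alongside it.

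Applied this way, the plan gives a sound NNAL comparison. The stated 98% power reproduces at the planned 50% retention. Carry-over from before the window would move the ratio to at most 0.319 even if half the PP subjects had a full smoking day 8 days before sampling. That shift raises NNAL in the CHTP 1.2 arm, so it does not inflate type I error. Exclusions are settled at a meeting before database lock, and the study statisticians stay blinded until SAP finalization or lock, whichever is later.

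This rests on the SAP's planning ratio and CV, first-order elimination with the protocol's half-lives, and lapse frequencies that are assumed because the documents give none. The textual conclusion needs none of these. It rests on each ambulatory period having a single assessment visit, which leaves the one-week paragraph with a purpose under only one of the two readings.

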11.2 Minor Protocol Deviations

The categories for the minor deviations may include, but are not limited to the deviations presented in **Table 13**.

Category	Description
Time deviation	Assessments not taken at the correct time or within the allowed time window (see Table 14)
Visit window deviation	Visits not performed within the allowed time window (see Table 14)
Time missing	Assessment date or time is missing
Procedural violation	A minor deviation in the conduct of a procedure
Duration of 24 hour urine collection	Urine collection period duration in [20h -23h[or]25h-28h] for Day -2, Day -1, Day 1, Day 2, Day 3 or Day 4, Day 5/Discharge from Confinement, Day 30 Visit, Day 60 Visit or Day 90 Visit
Assessment missing	Assessment is missing

11.3 Assessment Windows

Use of the randomized products in the confinement setting should take place within the 06:30 AM and 11:00 PM window. At Day 30 Visit, Day 60 Visit, and Day 90 Visit, subjects in the CHTP 1.2 and CC arms will be allowed to use their assigned product from the time of check-in until 11:00 PM. On the second day of Day 30 Visit and Day 60 Visit, product use will be allowed from 06:30 AM.

The assessment windows are shown in **Table 14**.

Assessment	Nominal Time point(s)	Window
24 h urine sample	Day -2 to Day 6	Day -2:prior to 11:30 AM on Day -2 (start) to after 24 hours ± 1 hour later on Day -1 (end). The end of the 24-hour urine should be prior to smoking the first CC. From Day -1 onwards until Day 6: start after the end of 24-hour urine collection of the previous day (after 24 hours ± 1 hour). The end of the 24-hour urine should be prior to smoking the first CC in the

**Table 14: Assessment Windows**

Assessment	Nominal Time point(s)	Window
	Day 30 Visit, Day 60 Visit and Day 90 Visit	CC arm and prior to use of the first CHTP 1.2 in the CHTP 1.2 arm. Start at 09:00 ± 30 minutes (after bladder void) until 24-hours ±1 hour later.
Spirometry	Screening Day 6 and Day 90 Visit	spirometry without bronchodilator: at least 1 hour after having stopped smoking and prior to spirometry with bronchodilator spirometry with bronchodilator performed 15-30 minutes post administration of salbutamol spirometry will be performed prior to product use (CC or CHTP 1.2). spirometry post-bronchodilator performed 15-30 minutes post administration of salbutamol Day 6: 06:29 AM ± 1.5h Day 91: prior to 11:30 AM
CYP1A2 activity	Day -1, Day 5 and Day 90 Visit	6 hours after intake of cup of coffee ± 15 min
CYP2A6 activity	Day -3, Day 6 and Day 90 Visit	Prior to smoking / product use Day -3 and Day 90 Visit (Day 91): prior to 11:30 AM Day 6: 06:29 AM ± 1.5h
CO breath test	Day -2 to Day 5 Day -3, Day 30 Visit, Day 60 Visit and Day 90 Visit	in the evening around 08:00 PM ± 1.5 hour in conjunction (i.e., within 30 minutes) with COHb tests. First day of the respective visits; irrespective of time of product use
Assessment of Cough	Day -2 to 6 Day 30 Visit, Day 60 Visit and Day 90 Visit	To be done prior to product use but not later than 11:30 AM Second day of the respective visits; prior to 11:30 AM; irrespective of time of product use
Nicotine and cotinine in plasma	Day -1 to Day 6	Day -1 to Day 5: between 08:00 PM ± 1.5 hour. Day 6: between 06:29 AM ± 1.5h.

**Table 14: Assessment Windows**

Assessment	Nominal Time point(s)	Window
	Day 30 Visit, Day 60 Visit and Day 90 Visit	Day 30 Visit, Day 60 Visit, and Day 90 Visit (first day of the respective visits): irrespective of the time of product use.
COHb blood sampling	Day -2 to Day 5, Day 30 Visit, 3 and 4	From Day -2 to Day 5: in the evening around 08:00 PM \pm 1.5 hour. At Day 30 Visit, Day 60 Visit, and Day 90 Visit (first day of the respective visits): irrespective of the time of product use.
mCEQ, QSU, ITUQ, Prochaska, FTND (as applicable)	Day -2 to Day 5, Day 30 Visit, Day 60 Visit and Day 90 Visit	08:00-11:00 PM
Clinical laboratory parameters, cardiovascular/oxidative stress clinical risk endpoints in blood (as applicable)	Screening, Day -1, Day 5, Day 6, Day 30 Visit, Day 60 Visit and Day 90 Visit	Prior to 11:30 AM on Day 1, Day 5 and Day 30 Visit, Day 60 Visit and Day 90 Visit (second day of the respective visit) Day 6: 06:29 AM \pm 1.5h

11.4 Invalid data

Data will be reviewed prior to locking the database. Assessments of endpoints will be reviewed for their potential invalidity. Examples of invalid assessments are:

- If the duration of urinary collection at a given timepoint is less than 20 hours or more than 28 hours, the urinary BoExp and urinary clinical risk endpoints at this timepoint would be considered invalid and not be considered in any analysis.
- CYP1A2, CYP2A6 or 11-DTX-B2 assessments within less than 5 $t_{1/2}$ after a medication with an impact on the CYP1A2, CYP2A6 or 11-DTX-B2 metabolism will be considered invalid and not be considered in any analysis.

12 Planned Statistical Methods

12.1 General Considerations

Data analysis will be performed using SAS[®] Version 9.2 or higher.

Data listings will be provided for all data collected as required by this protocol, ordered by arm and subject and timepoint (if applicable), unless otherwise stated. Summary statistics and statistical analyses will only be presented for data where detailed in this SAP. All unscheduled assessments will be included in the listings.

The protocol specifies that the assumptions of the analysis of variance model will be tested. The distribution of the data will be visually checked for normality or log-normality by means of histograms. Markedly non-(log)normally distributed data will be transformed or analyzed by appropriate non-parametric methods. For all endpoints, the assumed distribution is mentioned in the SAP.

For log-transformed endpoints, the least squares (LS) means and estimate of the difference along with its 95% CI will be back-transformed before presenting in the tables. The geometric LS means for each arm along with the reduction (i.e: 100% - ratio of CHTP 1.2 : CC (%)) and 95% CI will be presented in the tables. For naturally distributed data, the obtained LS Means for each arm along with the difference between these and 95% CI will be presented in the tables.

For data summarized on the log scale (or data summarized in its natural scale and for which a log transform was applied in an attempt to get normality), markedly non-lognormally distributed parameters will be analyzed with bootstrapping the log-transformed data using the SAS PROC SURVEYSELECT procedure. The seed to be used in any analysis will be contained in the SAS output and will be different for each analysis.

12.1.1 Stratified Presentation

For the analysis and descriptive statistics of the primary study endpoints, the following stratification criteria will be used:

1. Sex (male; female).
2. Average daily CC consumption over the 6 weeks prior to admission as reported on the Admission Day (smokers smoking 10 to 19 CC/day and smokers smoking > 19 CC/day).
3. Product use category: CHTP 1.2, Dual or CC in the CHTP 1.2 arm (see **Table 7**)

12.1.2 Subgroup Analyses

No subgroup analyses will be performed in this study.

12.1.3 Descriptive Statistics

For continuous data, summary statistics will include the number of subjects (n), the number and percent of subjects with missing data, the arithmetic mean, arithmetic SD, arithmetic mean 95% CI, median, first and third quartiles, minimum, maximum, and number of BLOQ values. For log-normally distributed data, the geometric mean, geometric mean 95% CI, and geometric CV will additionally be presented. For post-baseline non-transformed endpoints, the change will be shown; for post-baseline transformed endpoints, the percent change will be shown; unless otherwise specified.

For categorical data, frequency counts and percentages will be presented. Data listings will include all subject level data collected unless otherwise specified. Summary statistics and statistical analyses will generally only be performed for subjects included in the relevant analysis population. For the calculation of summary statistics and statistical analysis, unrounded data will be used.

Summaries on the Safety Population will be produced by actual exposure. The actual exposure differs from the exposure as randomized only for subjects who consistently used the wrong product; ie if the site had consistently administered the wrong product inadvertently. Subjects who tested the product but were discontinued before randomization will be shown in a separate column /table.

The following product labels will be used throughout the TFLs (**Table 15**):

**Table 15: Product Labels**

Product	Format used in TFLs	Order in TFLs
Carbon Heated Tobacco Product 1.2	CHTP 1.2	1
Combustible cigarette(s)	CC	2
Exposed not Randomized	Exposed	not 3
	Randomized	

The following stratification labels (**Table 16**) for the TFLs will be used:

Table 16: Stratification Labels

Stratification Factor	Definition
Sex	male female
Daily CC consumption (per day)	<10 ¹ 10-19 >19
Product use category.	CHTP 1.2 Arm: CHTP1.2 [70-100%] Dual]30-70%[CC [0-30%]

¹ Note that due to inclusion criteria for the study there should not be any subjects with daily CC consumption < 10, therefore this category will not be presented unless there is sufficient data for analysis/presentation (see Section 12.1.5.1 "Insufficient Data for Analysis/Presentation").

